Informed Consent: Written informed consent will be obtained from the participant prior to any study-specific activities either in person or remotely.

Assessments: Participants will complete a series of assessments at two timepoints; Time 1(baseline) will occur up to 2 years post-completion of primary treatment and before randomization and initiation of the exercise intervention/usual care. Time 2 will occur approximately within 1 month of completion of the intervention (or 7 months post-Time 1). Data collection at each timepoint will be composed of behavioral assessments, blood samples, neuroimaging and objective measures of physical activity and fitness. We will also objectively evaluate physical activity at 3 time points during participation (approximately every 5 weeks). For participants who agree to additional follow-up via the addendum consent form, Time 3 will take place approximately 6 months post Time 2 and will consist of blood work, fitness testing and behavioral testing as described below. We will also objectively evaluate physical activity at midway (3 months) between Time 2 and Time 3 as well as at Time 3. Participants will also be asked to maintain their edema cap and REDCap diaries during this time. Participants may be asked to complete assessments in two separate sessions at both TP1 and TP2. During one visit (which includes fitness testing), blood samples (approximately 30cc or 6 teaspoons) will be collected for biobanking for future evaluation of the relationships of biomarkers (including genetic biomarkers) with cognitive function, exercise, brain health and symptoms. Blood samples will be transported immediately, under conditions appropriate for preservation of the blood, and stored before the end of the day of testing. Samples will be maintained in a -80°C freezer in the Victoria building under the control of the principal investigators of this research project and will be maintained indefinitely. In the event that we need to send samples to a different facility outside of the University of Pittsburgh for analysis in the future, no identifying information will accompany the sample. Participants will be asked questions prior to the blood draw to determine any factors which may affect the findings. If a recent illness is noted, or certain other factors as noted on the form, are found, the participant may not be eligible for a blood draw at this visit. In this event, we will attempt to collect the blood at another time, either during a subsequent visit or other agreed upon time. Fitness will be objectively measured at Time 1 and Time 2. This test takes 15-30 minutes to complete. Subjects will be given exercise testing instructions regarding proper clothing and footwear and will be told to abstain from caffeine or nicotine 2 hours prior to the physical activity/fitness assessment. When participants report to the laboratory (Sennott Square) for the fitness assessment they will first be acquainted with the equipment, allowed to ask any questions, and get comfortable with walking on a treadmill. Before the test begins, the participant will get familiar with wearing the mouthpiece and nose clips or facemask required during the test in order to measure cardiovascular fitness. This helps to reduce anxiety associated with exercise and fitness testing. Cardiovascular fitness testing consists of progressively increasing exercise intensity while the subjects exhaled air is collected via a mouthpiece that is connected to a gas exchange chamber via a breathing tube. A comfort fitted head gear supports the mouthpiece. This reduces the effort of the participant to keep the mouthpiece in the correct position throughout the test. Alternatively, the participant may wear a facemask. The gas chamber that is being used is the Parvo Medics True one 2400 metabolic cart, which is one of the most widely accepted systems in scientific research. Next we will provide the participant with adequate warm-up and stretching which will be monitored by the exercise physiologist. After 5-10 minutes of warm-up, the participant will walk on a motor-driven treadmill at a constant speed with increasing increments of the incline. We will conduct a submaximal vo_2 fitness test which estimates the maximal oxygen capacity for the individual without reaching an exhaustive level. The sub-maximal graded exercise test is a modified Balke protocol in which the speed remains constant and grade is increased 1% each minute. This protocol has been used extensively in the literature for fitness training for both normal, at-risk, and impaired populations. Verifying maximal vo_2 is difficult in at-risk

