Analysis Plan for Aim 3. We will explore neuroimaging metrics of brain health, biomarkers, and symptoms as variables that may mediate the effects of the exercise intervention on cognitive function and E2 as a possible moderator. Initially, we will fit simple mediational models (predictor, single mediator, single outcome) applying the change score method and estimate whether effects of exercise (predictor) on changes in cognitive function outcomes are mediated through changes in the suspected mediators. Goodness-of-fit will be assessed through standard summary indices (e.g., RMSEA, CFI) and residual analyses. Total, indirect and direct effects will be estimated and reported with confidence intervals. Additionally, we will explore mediation applying the half-longitudinal approach proposed by Cole and Maxwell *ENREF_148* as well as an autoregressive mediational approach. Depending on the results from simple mediational modeling, we may also combine mediators into a multiple or serial mediator models to develop a more comprehensive picture of these pathways. As stated previously, voxel-based mediation of neuroimaging results will be conducted using BRAVO by employing the same approach described above. To explore E2 as a moderator of exercise effects on cognitive function, the models developed in Aim 1 will be expanded to also include E2 as main effect as well as interactions of E2 with the other fixed effects. Exploratory analysis. We will explore whether physical activity diary data are related to objective physical activity data. If validated, we will explore the physical activity patterns over 6 months and its relationship to change in outcomes.

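### The first Aim 3 mediation models relate two changes over the same interval and are saturated, so shared influences can pass as mediation and RMSEA and CFI cannot warn of it

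*Combined protocol and SAP*

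**What the plan says.** The Statistical Plan, under Analysis Plan for Aim 3, sets out a sequence.

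- First step: "simple mediational models (predictor, single mediator, single outcome) applying the change score method". The question is whether "changes in cognitive function outcomes are mediated through changes in the suspected mediators".
- Model check: "Goodness-of-fit will be assessed through standard summary indices (e.g., RMSEA, CFI) and residual analyses". Total, indirect and direct effects are reported with confidence intervals.
- Further approaches: "Additionally, we will explore mediation applying the half-longitudinal approach", "as well as an autoregressive mediational approach".
- Extension: depending on what the simple models show, "we may also combine mediators into a multiple or serial mediator models".

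Under Research activities, Assessments, the core study has two timepoints. Women who sign an addendum consent have a third: "Time 3 will take place approximately 6 months post Time 2 and will consist of blood work, fitness testing and behavioral testing". Behavioral testing includes the neuropsychological battery, so cognition is available at TP3. The neuroimaging text places MRI at TP1 and TP2 only. The Statistical Plan does not mention TP3, states no assumption about confounding of mediator and outcome, and plans no sensitivity analysis for it. Specific aims and the Aim 3 plan both describe this work as exploring.

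**The concern.** An indirect effect is the product of two paths. Random allocation makes the first, exercise to mediator, a fair comparison. The second, mediator to cognition, is an observational association within arms. When both variables are changes over the same interval, two things other than mediation can create it:

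- influences shared by the two measurements at a timepoint, such as a bad week that affects both reported fatigue and test performance;
- a stable factor that moves both the mediator and cognition after baseline.

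Either, combined with a real effect of exercise on the mediator, gives a non-zero product.

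The planned fit check looks like a safeguard but cannot be one for this model. A report could list an indirect effect with an interval excluding zero beside a perfect RMSEA and CFI, and a reader would take the second as support for the first. The simple models also decide which larger models are built, so an early false lead can be carried forward.

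**Working it through.** The documents give no significance level, effect size, SD or correlation for Aim 3, so there is no stated figure to reproduce.

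**1. Degrees of freedom.** Three variables give 3 × 4 / 2 = 6 variances and covariances. The model has three paths (group to mediator, mediator to cognition, group to cognition), one group variance and two residual variances: 6 parameters. Hence df = 6 − 6 = 0. Fitted to data generated forward, in reverse order and by confounding alone, the model gave chi-square 0 each time, so RMSEA = 0 and CFI = 1 by construction. Some other planned models are also saturated and some are not. A full two-mediator serial model has 10 − 10 = 0. Two parallel mediators have 10 − 9 = 1 if their residual covariance is fixed at zero, and 0 if it is freed.

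**2. How often shared influence passes as mediation.** From the documents: up to 127 women per arm, and 75 per group for imaging. Assumed: two-sided 5% tests, both paths required to be significant, full retention, total SD 1 split into trait variance 0.6 and occasion variance 0.4, exercise effect on the mediator a = 0.4 SD, true mediator effect zero. Let r be the within-arm correlation of the two changes.

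The trait part cancels in a change score, so its SD is √(2 × 0.4) = 0.894.

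- Path a: z = a / (0.894 × √(2/n)). At n = 127, 0.4 / (0.894 × 0.1255) = 3.56, significant with probability 0.946. At n = 75, 0.4 / (0.894 × 0.1633) = 2.74, probability 0.782.
- Path b: z = r√(N − 3) / √(1 − r²), with N = 254 or 150. At r = 0.3 this is 4.98 or 3.81 (probability 0.999 or 0.968). At r = 0.1 it is 1.59 or 1.22 (0.357 or 0.230). At r = 0 the probability is 0.05.
- The false indirect effect is a × r, for example 0.4 × 0.3 = 0.12 SD.

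| r | 127 per arm | 75 per arm |
|---|---|---|
| 0 | 0.946 × 0.050 = 5% | 0.782 × 0.050 = 4% |
| 0.1 | 0.946 × 0.357 = 34% | 0.782 × 0.230 = 18% |
| 0.3 | 0.946 × 0.999 = 94% | 0.782 × 0.968 = 76% |

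Simulations of the same setting agree: 3 to 5% at r = 0, 32 to 34% and 18% at 0.1, 94 to 95% and 74 to 76% at 0.3. With a = 0.1 SD and r = 0.3 the rates fall to about 15% and 11%, because path a is then rarely significant.

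**3. Do the other planned models settle it?** At r = 0.3, simulated:

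- Adjusting the TP2 outcome for TP1 values does not help: 96 to 98% and 76 to 78%.
- The half-longitudinal model is falsely positive in about 30% and 15 to 18%, with a negative indirect effect. Its mediator-to-cognition path uses the TP1 mediator, which precedes randomization, so it must assume that the same relation holds after treatment starts.
- With two waves, an autoregressive model has no post-randomization mediator measure that comes before the outcome measure.

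**4. What would TP3 add?** With TP3 cognition regressed on the TP2 mediator, group, TP1 mediator and TP1 cognition, false mediation at r = 0.3 is 18 to 19% and 12%. Adding TP2 cognition brings it to about 7% and 6%. These figures assume everyone attends TP3. A stable confounder of both changes is a different matter. With confounder variance 0.1, no shared-timepoint influence, a = 0.5 SD and 127 per arm, the change-score model is falsely positive in 42%, the TP3 model without TP2 cognition in 58%, and the TP3 model with it in 26%.

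**The case against.** **Other mediation models are planned.** This stands against any reading that all of Aim 3 relates concurrent changes; that describes the first step only. But the additional models do not establish order with two waves, and the plan does not say which governs if they disagree. The autoregressive model might be meant to use TP3, but the Statistical Plan does not say so, and MRI has no third wave.

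**Shared influence need not be large.** A reader might infer that mediator and cognition are measured on the same day. The documents do not support that. Assessments may be split over two sessions, MRI is at another institution, and a blood draw can be postponed after recent illness. The accurate term is same timepoint. Shared influence is most plausible for symptoms and least for regional brain volume. Fatigue, sleep and mood are themselves candidate mediators and could be modeled jointly. Influences lasting days or weeks, and stable confounders, remain.

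**The high rates come from the inputs.** This stands. At r = 0.3 the second path is almost always significant, so the 95% is essentially the power to detect the assumed exercise effect on the mediator. That is why the range from r = 0 is shown.

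**The fit check is not wholly empty.** Perfect fit is automatic only for saturated models, and the planned residual analyses can still show outliers and nonlinearity.

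**Aim 3 is exploratory.** Agreed. Building larger models after simple ones is normal in such work.

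**Conclusion.** The point holds for the initial change-score models. They cannot separate mediation from shared or stable confounding of the two changes, their RMSEA and CFI carry no information, and no planned analysis examines the mediator-to-cognition assumption. The saturation result is arithmetic and needs no assumption about the trial. The false-mediation rates rest on the assumed variance split, exercise effect and correlation; they give direction and range only.

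One might go further and conclude that TP3 cognition should anchor the main Aim 3 model. The documents do not support that. TP3 is opt-in with no stated size, and nothing says how many women, or how many with MRI, have it. It falls about six months after TP2, once the intervention has ended, so it concerns persistence rather than the first six months of therapy. Without TP2 cognition in the model, it did worse than change scores under a stable confounder. The consequence is for the interpretation of an exploratory aim, not for the primary result.

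**What to change.** Amend Analysis Plan for Aim 3 as follows.

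1. State that RMSEA and CFI will not be offered as support for single-mediator or other saturated models. Keep the residual analyses.
2. Report change-score indirect effects as associations. Add a sensitivity analysis for unmeasured mediator-outcome confounding, for instance by varying the assumed residual correlation between the mediator and outcome equations and reporting the value at which the indirect effect disappears. In the illustration with r = 0.3, that value is 0.3.
3. In women with TP3 data, add a supportive analysis regressing TP3 cognition on the TP2 mediator, adjusted for group, TP1 mediator, TP1 cognition and TP2 cognition. TP2 MRI measures can be used in the same way.
4. Say how results will be read if the change-score, half-longitudinal and autoregressive models disagree.

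The cost is SAP wording and modest extra analysis; the protocol already provides for the TP3 assessments. The TP3 model has real limits: a self-selected subset of unknown size, wider intervals, a later target, and no removal of stable confounding. Adjusting for TP2 cognition also leaves out any mediator effect already expressed by TP2. Items 1, 2 and 4 need no TP3 data and are worth doing in any case.
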